1. SYNOPSIS

Title:	Phase II study of pembrolizumab plus ramucirumab in metastatic gastric or GEJ adenocarcinoma as salvage treatment
Design:	A single-arm, open-label, single-center Phase II study
Sponsor:	Samsung Medical Center Principal Investigator :[name] M.D, Ph.D.
Objective	
1) Primary Objective: To estimate preliminary overall response rate (ORR) of combination therapy of Ramucirumab and Pembrolizumab in patients with metastatic gastric or GEJ adenocarcinoma
 
2)Secondary Objectives: To assess secondary measures of clinical efficacy
 
 - Best Overall Response Rate: BORR - Disease Control Rate: DCR - Progression-Free Survival:PFS - Overall Survival: OS - Duration of Overall Response: DOR & maximal tumor shrinkage 
3) Biomarker Objectives: Integrative immune-genomic analysis to identify association of response with prevalent markers (e.g. PD-L1 expression, EMT signature, T-cell and cytolytic immune signatures, RNA-seq, hypermutation, pre and post cfDNA cancer panel genomics (Changes of TMB and landscape of genome), PFS/OS/safety
 
 ✓ Fresh tissues at baseline if clinically feasible/ in advanced to 3 cycles(if clinically feasible) ✓ (archival tissue only is not acceptable for study entry due to limited analysis on archival tissues) ✓ RNA sequencing to understand the mechanism of action of pembrolizumab and ramucirumab in responders and non-responders. ✓ Evaluating changes of component of Immune cells and cytokines in blood. ✓ Describe the association between EBV gastric cancer /or high PDL1 MSS and clinical activity in subjects who metastatic gastric or GEJ adenocarcinoma.
Subjects:	Patients with metastatic gastric or GEJ adenocarcinoma; EBV positive or PDL1 CPS≥5 .
Inclusion & Exclusion Criteria	
Inclusion Criteria
 
Each patient must meet the following criteria to be enrolled in this study:
 
 1. The patient is ≥18 years of age.

[Type here]

[Type here]

[Type here]

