4.4.1 Immunotherapy in GC

[figure not shown]
Pembrolizumab is a selective, humanised, high-affinity IgG4-κ monoclonal antibody designed to bind to PD-1 and thus block the interaction between PD-1 and its ligands.⁴ Pembrolizumab has a manageable safety profile and has shown promising anti-tumour activity in several types of advanced solid tumours and hematological malignancies, raising hopes that this therapy may have efficacy in gastric cancer.⁵ Indeed, genomic sequencing analysis across multiple tumors demonstrated that gastric adenocarcinoma commonly possess relatively high mutational load, suggesting the presence of novel tumor antigens which could mark patients who may respond to pembrolizumab or other immune checkpoint inhibitors⁶.

Pembrolizumab (Keytruda®, Merck) is currently approved in the US for the treatment of GC and nivolumab (Opdivo®) has been approved in Japan and Korea for salvage treatment in GC. Early trials demonstrating the potential for PD-1 therapy in GC were performed in patients with positive immunohistochemical expression of PD-L1, a ligand for PD-1 ^{7,8}. In KEYNOTE-012 trial, 39 PDL-1-positive GC patients with chemotherapy-refractory metastatic disease were treated with pembrolizumab and 8 patients had a response (22%, 95% CI 10 – 39), including 8 partial responses and 0 complete response⁹. A subsequent study, the KEYNOTE-059 (NCT#02335411) phase II trial of pembrolizumab in an unselected population of metastatic GC patients who specifically

[Type here] [Type here] [Type here]

Pembrolizumab + Ramucirumab(Ver 2.5, Oct 2024)
received 2 prior lines of therapy (n=133) demonstrated an overall response rate (ORR) of 16.4%10.

In a recent collaborative project with Merck on phase II pembrolizumab trial in metastatic GC, we have found that dramatic responders are EBV+, high mutational load, or MSI-high patients (Nature Medicine 2018 published July 16 2018, Waterfall chart).

In recent our study, CR was achieved in 3 patients (4.9%, 95% CI: 1.3–13.7), 12 patients achieved confirmed PRs (PR; 19.7%, 95% CI: 10.6 – 31.8), and 20 patients (32.8%, 95% CI: 21.3–46.0) had stable disease, resulting in an ORR of 24.6% (95% CI: 14.7 – 37.3) and a disease control rate (DCR) of 57.4% (95% CI 44.1-70.0). This response rate of 24.6% was consistent to previous other immunotherapy-trials in GC. (Kim ST/Lee J et al Nature Medicine 2018 July 16 published)

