5.0 Objective

5.1 Primary Objective:

To estimate preliminary overall response rate (ORR) of combination therapy of Ramucirumab and Pembrolizumab in patients with metastatic gastric or GEJ adenocarcinoma

5.2 Secondary Objectives:

To assess secondary measures of clinical efficacy

- Best Overall Response Rate:BORR

[Type here]

[Type here]

[Type here]

Pembrolizumab + Ramucirumab (Ver 2.5, Oct 2024)

- Disease Control Rate: DCR
- Progression-Free Survival: PFS
- Overall Survival: OS
- Duration of Overall Response: DOR & maximal tumor shrinkage

5.3 Biomarker Objectives:

Integrative immune-genomic analysis to identify association of response with prevalent markers (e.g. PD-L1 expression, EMT signature, T-cell and cytolytic immune signatures, RNA-seq, hypermutation, pre and post cfDNA cancer panel genomics (Changes of TMB and landscape of genome), PFS/OS/safety

- ✓ Fresh tissues at baseline pre-treatment if clinically feasible and before 3 cycles if clinically feasible)
- ✓ (archival tissue only is not acceptable for study entry due to limited analysis on archival tissues)
- ✓ RNA sequencing to understand the mechanism of action of pembrolizumab and ramucirumab in responders and non-responders.
- ✓ Evaluating changes of component of Immune cells and cytokines in blood
- ✓ Describe the association between EBV gastric cancer /or MSI and clinical activity in subjects who metastatic gastric or GEJ adenocarcinoma.

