7. CARE PLAN

7.1 Study Design and Plan

This study is a single arm, open label, single center phase II study of ramucirumab in combination with pembrolizumab in EBV+ or CPS≥5 patients with advanced gastric adenocarcinoma including gastric adenocarcinoma or GEJ adenocarcinoma as a second or third line chemotherapy

[figure not shown]
Patients will receive ramucirumab plus pembrolizumab combination regimen. This study recruits a maximum of 35 patients.

Lilly will only supply ramucirumab and Merck will supply pembrolizumab. Lilly and Merck will not supply other medications used in the care of patients while on this study.

Patients will receive ramucirumab, administered via intravenous (I.V.) infusion over approximately 1 hour, every 2 weeks, at a dose of 8 mg/kg, and pembrolizumab 200 mg will be administered as a 30 minute IV infusion every 3 weeks. (pembrolizumab first followed by

[Type here] [Type here] [Type here]

Pembrolizumab + Ramucirumab(Ver 2.5, Oct 2024)
ramucirumab when concurrently administered on the same day)
- Ramucirumab 8mg/kg on q2W
- Pembrolizumab 200mg on q3W

Assessment of disease control is recommended every 6 weeks (every cycle).

It is recognized that in the course of clinical cancer care, it is not always possible to schedule therapeutic infusions precisely 2 weeks-ramucirumab/3 weeks-pembrolizumab following a prior infusion (because of holidays, travel difficulties, or other circumstances). Accordingly, infusions administered within 3 days before or after the planned time point are acceptable. Administration beyond this window is strongly discouraged.

All patients may continue to receive treatment with the IP, ramucirumab, until there is evidence of progressive disease (PD), unacceptable toxicity, the patient is withdrawn from the study for any other reason, or ramucirumab becomes commercially available and accessible to patients after local marketing authorization. Also, if ramucirumab stops then pembrolizumab be discontinued as well.

Treatment may be discontinued as outlined in Section 6.3

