7.2 Enrollment/screening Period

The following assessments and procedures should be performed within 28 days prior to first dose of study treatment. For details of the schedule and nature of the assessments, see below.

- Signed informed consent for the study; include main inform consent
- Results of EBV IHC or PDL1 (EBV positive or PDL1 CPS≥5)

EBV test: (all centralized at CAP-certified pathology lab/SMC): he entire procedure was performed on a fully automatic system (BOND-MAX) for in situ hybridization with an EBV-encoded RNA probe from Leica (Newcastle, UK) following manufacturer's instructions (ref: Gastroenterology [Type here] [Type here] [Type here])

Pembrolizumab + Ramucirumab (Ver 2.5, Oct 2024)
2010 vol 139, pages 84-92).

PDL1 test: IHC staining will be carried out on Dako Autostainer Link 48 system (Agilent Technologies, Santa Clara, CA) using Dako PD-L1 IHC 22C3 pharmDx kit (Agilent Technologies) with EnVision FLEX visualization system and counterstained with hematoxylin according to the manufacturer's instructions. PD-L1 protein expression will be determined by using Combined Positive Score (CPS), which was the number of PD-L1 staining cells (tumor cells, lymphocytes, macrophages) divided by the total number of viable tumor cells, multiplied by 100. (ref: https://www.agilent.com/cs/library/usermanuals/public/29158_pd-l1-ihc-22C3-pharmdx-nslcl-interpretation-manual.pdf)

- Date of birth, race and ethnicity
- Medical and surgical history
- Current and concomitant medications including previous cancer therapies (if applicable)
- Physical examination
- ECOG performance status
- Vital signs (blood pressure, pulse and body temperature), body weight and height.
- Hematology, clinical chemistry and urinalysis, TFT
- Menopausal status; serum or urine pregnancy test for women of childbearing potential (within 7 days prior to study treatment start
- ECG
- Echocardiogram/MUGA Should be completed if patients had received prior anthracycline therapy
- Tumor assessment (scans of the abdomen/pelvis/other sites as clinically indicated for assessment of disease [CT/MRI]), performed within 14 days prior to enrollment, ideally should be performed as close as possible to the start of the treatment. Scans that were performed as part of standard of care prior to signature of the informed consent form can be analysed for the purposes of the study if they were performed within the correct time frame and consistent with modified RECIST guidelines for CT or MRI

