10.3 Biomarker Evaluation

We will conduct Biomarker Research on specimens collected during this clinical trial. This research may include genetic analyses(DNA), gene expression profiling (RNA), proteomics, metabolomics (serum, plasma) and/or the measurement of other analytes.

Genomic analysis: Whole Exome Sequencing at baseline if it is feasible, RNA-seq pre and post (Whole Exome Sequencing/RNA sequencing will be performed at SMC using vendor (Macrogen INC., Korea) and analyzed together with the BI team at SMC with Merck MSD or Lilly.

The objective of collecting specimens for Biomarker Research is to explore and identify biomarkers that inform the scientific understanding of diseases and/or their therapeutic treatments. Integrative genomic analysis (i.e. gene signature, etc.) measured may be a predictive biomarker for patients who receive pembrolizumab treatment.

Integrative immune-genomic analysis to identify association of response with prevalent markers (e.g. PD-L1 expression, EMT signature, T-cell and cytolytic immune signatures, RNA-seq, hypermutation, cfDNA cancer panel genomics).

Pre and post (on-drug biopsy at 6 weeks): RNA sequencing and cfDNA cancer panel genomics to understand the mechanism of action of pembrolizumab/ramucirumab in responders and non-responders.

Pre and post (at baseline, at 3-week and at 6-week post-treatment) to evaluating immune-priming effect of chemotherapy alone and pembrolizumab:

- i) The assessment of plasma or cell free tumor DNA (ctDNA) variant allele frequency (VAF) and tumor mutation burden (TMB) at baseline, at 3-week and at 6-week post-treatment;
- ii) The assessment of integrated molecular profiling (including T cells-

[Type here]

[Type here]

[Type here]

Pembrolizumab + Ramucirumab(Ver 2.5, Oct 2024)

CD3+,CD8+,CD45RO+, Tregs-FOXP3+ and macrophages-CD163+, MHC-1, and PDL1 expression) will be assessed using single cell sequencing (blood and tissue) via 10X genomics.

As an exploratory analysis, we will isolate T cells using FACS sorting and sequence these cells. In addition, in order to identify the relationship between neoantigen drivers like infection and response to pembrolizumab, we will prospectively collect serum antigens from blood at baseline. FACS (Cytex) 20-panel antibody will be used.

11. Adverse Events and Dose Modification

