12. SAMPLE SIZE

Sample Size Calculation

[Type here]

[Type here]

[Type here]

Pembrolizumab + Ramucirumab(Ver 2.5, Oct 2024)

A maximum of 26 patients will be recruited to this single-arm phase II trial. The primary endpoint of this trial is overall response (OR=PR+CR).

In this single-arm phase II trial, 25 people were calculated using Simon's two-stage design and a total of 26 patients will be recruited to account for a 5% dropout rate.

The sample size is calculated by use of a two-stage minimax Simon's design to control the type I error at 5 % for null hypothesis that, for arm, the true response was 15 % or below and to have 85 % of power if the true response was 40 % or higher. 15 evaluable patients are to be treated in the first stage. If 1 or fewer response are observed in the first stage, the arm will be stopped. If at least 2 responses are observed in the first stage, 10 additional evaluable patients are to be entered onto the second stage. At the final analysis, the null hypothesis will be rejected if at least 7 responses are observed in 25 evaluable patients. RR is reported with its exact 95% CI.

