13.1.2 Biomarker

To explore and identify biomarkers (inform the scientific understanding of diseases and/or their therapeutic treatment), the contingency tables will be presented by response for each of tumor histology, molecular signatures, immune pathways and etc..

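### Entry on EBV+ or CPS≥5 leaves one EBV-by-PD-L1 cell empty, so response tables taken one marker at a time mix the EBV and PD-L1 associations and can be biased against high PD-L1

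*Combined protocol and SAP*

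**What the plan says.** Section 7.1 describes the trial as being "in EBV+ or CPS≥5 patients with advanced gastric adenocarcinoma". The screening list in section 7.2 asks for "Results of EBV IHC or PDL1 (EBV positive or PDL1 CPS≥5"), then describes the EBV assay and the PD-L1 assay in turn.

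Several places ask how these markers relate to outcome:

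- Section 10.3 plans: "Integrative immune-genomic analysis to identify association of response with prevalent markers (e.g. PD-L1 expression, EMT signature" and others. Section 5.3 and the synopsis carry the same aim.
- The synopsis adds: "Describe the association between EBV gastric cancer /or high PDL1 MSS and clinical activity".
- Section 5.3 words that objective differently: "Describe the association between EBV gastric cancer /or MSI and clinical activity".

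The biomarker part of the SAP (13.1.2) is one sentence, under which "the contingency tables will be presented by response for each of tumor histology, molecular signatures, immune pathways" and an open-ended remainder. It contains no EBV-by-CPS cross-table, no stratified comparison, no model and no comment on the entry rule. The planned size is set in section 12: "25 people were calculated using Simon's two-stage design and a total of 26 patients will be recruited to account for a 5% dropout rate".

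On the expected direction of the EBV association, section 4.4.1 reports from an earlier pembrolizumab trial that "we have found that dramatic responders are EBV+, high mutational load, or MSI-high patients".

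**The concern.** Selecting on either of two markers makes them dependent in the enrolled sample, whatever their relation in the disease at large. A PD-L1 table cut at CPS 5 sets a group that is entirely EBV-positive (CPS<5) against a group that includes all the EBV-negative patients (CPS≥5). If EBV status carries a response advantage, that advantage is credited to low PD-L1. The EBV table has the mirror-image problem, because its EBV-negative group is entirely CPS≥5.

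What is at stake is the set of marker associations that the biomarker objectives ask for. A reader of a one-way table could conclude that high PD-L1 predicts a poorer response to this combination when the pattern comes from eligibility alone. This is a bias and not just noise, so a larger sample with the same mix would not remove it.

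**Working it through.** Section 13.1.2 states no figure to reproduce. The inputs from the documents are the entry rule (7.1, 7.2), the 25 evaluable patients (12) and the direction of the EBV association (4.4.1). Cell sizes and response rates are not given, so those below are assumptions.

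**Notation**

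- p11 = response rate in EBV+/CPS≥5; p10 = in EBV+/CPS<5; p01 = in EBV-negative/CPS≥5. The fourth cell is empty by design.
- w = EBV-positive share of the CPS≥5 patients.
- d = p11 − p10, the PD-L1 effect within EBV-positive patients.
- E = p11 − p01, the EBV effect within CPS≥5 patients.

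**What the one-way PD-L1 table estimates**

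Crude difference (CPS≥5 minus CPS<5) = w·p11 + (1−w)·p01 − p10 = d − (1−w)·E.

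The table is biased downward whenever E > 0. For d > 0 the sign reverses only if (1−w)·E > d.

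**Case 1: no PD-L1 effect (d = 0), EBV-negative rate 25%.** The crude difference is −(1−w)·E. Cells are in the order EBV+/CPS≥5, EBV+/CPS<5, EBV-negative/CPS≥5.

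| Cells | 1−w | EBV+ rate 60% (E = 35) | EBV+ rate 40% (E = 15) | EBV+ rate 30% (E = 5) |
|---|---|---|---|---|
| 3/2/20 | 20/23 = 0.870 | −30.4 | −13.0 | −4.3 |
| 5/3/17 | 17/22 = 0.773 | −27.0 | −11.6 | −3.9 |
| 8/4/13 | 13/21 = 0.619 | −21.7 | −9.3 | −3.1 |
| 12/4/9 | 9/21 = 0.429 | −15.0 | −6.4 | −2.1 |

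In full for 5/3/17 at 60%: CPS≥5 rate = (5×0.60 + 17×0.25)/22 = 0.330; CPS<5 rate = 0.60; difference −27.0 points. By exact binomial enumeration, high PD-L1 would look worse in 81% of such trials.

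**Case 2: a real PD-L1 benefit of +20 points within EBV-positive patients**, with p11, p10, p01 = 70%, 50%, 30%, so E = 40 points.

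- 3/2/20: 20 − 0.870×40 = −14.8
- 5/3/17: 20 − 0.773×40 = −10.9 (39.1% against 50.0%)
- 8/4/13: 20 − 0.619×40 = −4.8
- 12/4/9: 20 − 0.429×40 = +2.9

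For 5/3/17 the observed difference is negative in 61% of trials from the one-way table, against 29% when the comparison is made within EBV-positive patients.

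**Case 3: EBV adds little**, with rates 60%, 40%, 55%, so E = 5 points. The crude difference is +15.7 to +17.9 across the same cells, against a true +20. There is attenuation but no reversal.

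**The EBV table.** With v the CPS≥5 share of EBV-positive patients, the crude EBV difference is E − (1−v)·d. For 5/3/17 and 70/50/30%, this is 40 − (3/8)×20 = 32.5 points against a true 40.

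**Precision.** With 2/3 responders in CPS<5 and 7/22 in CPS≥5, Fisher's exact p is 0.53. Exact 95% intervals are 9–99% for 2/3 and 28–99% for 4/5. In Case 1 with 5/3/17 and 60%, an inverse association with p<0.05 would arise in about 8% of trials.

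**The case against.** The strongest reply is that section 13.1.2 names neither PD-L1 nor EBV and sets no CPS cut, so a CPS≥5 versus <5 table is an inference. That is correct as far as it goes. However, the list in 13.1.2 is open-ended, PD-L1 expression heads the markers in section 10.3, EBV is an objective in its own right, and tabulating for each marker is the only method given. The integrative analysis named elsewhere comes without a method, so nothing in the plan prevents the problem.

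A second reply is that the analysis is exploratory, carries no test or decision, and may rest on about three CPS<5 patients. This also stands. It limits how much harm a misleading table could do, but it does not correct the direction of the bias.

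Four stronger readings are tempting, and the documents do not support them:

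- *The PD-L1 table will show the wrong sign.* Reversal needs (1−w)·E > d. It fails with cells 12/4/9 at 70/50/30%, and it fails throughout Case 3. Case 1 shows a spurious difference, not a reversal, because no true effect exists to reverse.
- *The overall ORR cannot be interpreted.* The primary test compares the response rate of the whole enrolled population with 15% and needs no marker breakdown.
- *Patients will enter with the other marker untested.* The conjunction in 7.2 can be read as stating what qualifies, and the same section describes both assays. The text does not say that both results are recorded for everyone, and that is all that can be claimed.
- *MSS status cannot be obtained.* Section 10.3 plans baseline whole exome sequencing where feasible and a cfDNA panel. What is missing is a definition and a named source of MSI status. Neither 7.2 nor Appendix 1 lists an MSI test, and the documents do not say whether the cfDNA panel can determine MSI.

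**Conclusion.** The concern holds in a conditional form. The empty cell follows directly from the entry rule. One-way response tables for PD-L1 and EBV therefore mix the two associations, and a PD-L1 table cut at CPS 5 is biased against high PD-L1 to the extent that EBV-positive patients respond more often. Section 4.4.1 supports that direction but gives no EBV-specific rate, and it comes from pembrolizumab without ramucirumab.

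The size depends wholly on assumed inputs. The bias could be large enough to mislead or small enough to ignore, and the plan gives no basis for choosing between those ends of the range. Reversal of a true benefit is possible, not assured. If no EBV+/CPS<5 patient enrols, the table has no comparison group at all.

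The differing wording of the EBV objective in the synopsis and section 5.3 is a plain inconsistency. The point as a whole merits a change to the plan because the remedy is simple. It concerns the exploratory biomarker analysis only.

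**What to change.** 1. In 13.1.2, report response in three exclusive groups: EBV+/CPS<5, EBV+/CPS≥5 and EBV-negative/CPS≥5. Compare PD-L1 only within EBV-positive patients, and EBV only within CPS≥5 patients. CPS may also be examined as a continuous value within EBV-negative patients, over the range from 5 upward. State that CPS≥5 versus <5 is not estimable in EBV-negative disease.
2. In 7.2, make clear that both the EBV and the CPS result are recorded for every patient, while either one alone still qualifies.
3. Use one wording of the EBV objective in the synopsis and 5.3, and name the source and definition of MSI status.
4. Report the primary ORR together with the EBV/CPS mix of the enrolled patients.

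The cost is SAP and protocol wording, plus recording the second marker result where it would not otherwise be available. Eligibility, sample size and the primary test do not change. The downside is very small cells, so the three-group results should be labelled descriptive and shown as counts with exact intervals.

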13.2 Safety

Safety will be assessed by clinical review of all relevant parameters including, adverse events (AEs), laboratory tests, vital signs, etc.

No statistical hypothesis tests will be performed on safety variables. These will be summarized by descriptive statistics or categorical tables.

14.Clinical Tests

14.1 Laboratory Parameters

All laboratory tests will be performed at local labs and should be done to ensure patients meet all eligibility criteria and criteria to continue on the protocol:

Hematology Profile – Includes a complete blood count with differential and platelet count.

[Type here]

[Type here]

[Type here]

Pembrolizumab + Ramucirumab (Ver 2.5, Oct 2024)

Coagulation Profile – Includes INR, prothrombin time, and PTT.

Chemistry Profile – Includes creatinine, AST, ALT, alkaline phosphatase, total protein, and bilirubin.

NOTE: If pretreatment serum creatinine is >1.5 times the ULN, calculate creatinine clearance

Urinalysis – Includes routine UA or dipstick measurements and, if clinically indicated, microscopic analysis

Serum -HCG Pregnancy Test – Minimum sensitivity 25 IU/L or equivalent units of β -HCG, to be performed within 28 days prior to enrollment for WOCBP.

TFT Test - T3, FT4 and TSH

